#### 5.4.5. Recommended Dose Modifications

Every effort should be made to administer study treatment on the planned dose and schedule.

In the event of significant toxicity dosing may be delayed and/or reduced as described below. In the event of multiple toxicities, dose modification should be based on the highest-grade toxicity observed. Patients are to be instructed to notify investigators at the first occurrence of any adverse symptom.

Dose modifications may occur in three ways:

- Within a cycle: dosing interruption until adequate recovery and dose reduction, if required, during a given treatment cycle.
- Between cycles: next cycle administration may be delayed due to persisting toxicity when a new cycle is due to start.
- In the next cycle: dose reduction may be required in a subsequent cycle based on toxicity experienced in the previous cycle.

## 5.4.5.1. Infusion Reactions

Following the first infusion of some monoclonal antibody therapeutics, some patients experience fever, headache, nausea, vomiting or hypotension. These adverse events (AEs) are generally ascribed to lysis of cellular targets, cytokine release, or complement activation.

In the case of infusion reaction, characterized by fever and chills, and less commonly hypotension, either experienced by a particular patient or if seen in other patients, pretreatment medication should be administered to reduce the incidence and severity. A regimen is suggested here; however, if local standard of care is a different regimen, this will be allowed. In cases of infusion reactions, patients should be pretreated with acetaminophen and diphenhydramine (or other antihistamine) approximately 0.5 to 2 hours before investigational product administration. The pretreatment medications will not be supplied by Pfizer. Suggested starting doses are 650 to 1000 mg acetaminophen and 50 mg

diphenhydramine (or equivalent for other antihistamines) either IV or oral. Two (2) additional doses of acetaminophen may be administered approximately every 4-6 hours after the initial pretreatment or as needed.

#### **5.4.5.2.** Hypersensitivity Types 1 and 3

Type 1 hypersensitivity or allergic (eg, shortness of breath, urticaria, anaphylaxis, angioedema) reactions are theoretically possible in response to any injected protein. Immune complex mediated Type 3 hypersensitivity reactions are similar to the adverse events (AEs) of Type 1 reactions but are likely to be delayed from the time of infusion and may include symptoms such as rash, urticaria, polyarthritis, myalgias, polysynovitis, fever, and, if severe, glomerulonephritis.

All patients should be closely observed while receiving investigational product infusions and monitoring for clinical signs of a systemic reaction will continue thereafter for clinical signs of allergic reactions/hypersensitivity.

In the case of a hypersensitivity reaction, the patient will be treated symptomatically with supportive care, further monitoring, and treatment with anti-histamines and/or corticosteroids. Study infusions may be stopped and the patient will be followed until the end of the study.

Detailed guidance on treatment, dose interruptions and potential retreatment is provided in Appendix 4.

#### 5.4.5.3. Extravasation

In the event of extravasation infusion should be stopped immediately and the investigator needs to be consulted immediately. Treatment of extravasation should follow local standard of care

#### 5.4.5.4. Immune-Related Adverse Events (irAEs)

Although the mechanism of OX40 and 4-1BB are different from check point inhibitors, both OX40 and 4-1BB do stimulate the immune system and thus immune-related AEs (irAEs) can occur. Immune mediated etiology of an AE will be adjudicated by the investigator. Treatment of irAEs is mainly dependent upon severity (NCI CTCAE grade v4.03):

- Grade 1 or 2: treat symptomatically or with moderate-dose steroids, more frequent monitoring;
- Persistent Grade 2: manage similar to Grade 3 to 4 AE;
- Grade 3 or 4: treat with high-dose corticosteroids.

Treatment of irAEs should follow guidelines set forth in Table 4.

 Table 4.
 Management of Immune-Related Adverse Events (irAEs)

Gastrointestinal irAEs					
Diarrhea / Colitis (NCI CTCAE v4.03)	Management	Follow-up			
Grade 1 Diarrhea: <4 stools/day over baseline; Colitis: asymptomatic	Continue investigational product therapy Symptomatic treatment (eg, loperamide)	Close monitoring for worsening symptoms Educate patient to report worsening immediately If worsens: Treat as Grade 2 or 3/4			
Grade 2 Diarrhea: 4 to 6 stools per day over baseline; IV fluids indicated <24 hours; not interfering with ADL Colitis: abdominal pain; blood in stool	Delay investigational product therapy Symptomatic treatment	If improves to Grade 1: Resume investigational product therapy If persists >5-7 days or recur: 0.5 to 1.0 mg/kg/day methylprednisolone or equivalent When symptoms improve to Grade 1, taper steroids over at least 1 month, consider prophylactic antibiotics for opportunistic infections, and resume investigational product therapy per protocol. If worsens or persists >3 to 5 days with oral steroids: Treat as Grade 3 to 4			
Grade 3 to 4  Diarrhea (Grade 3): ≥7 stools per day over baseline; incontinence; IV fluids ≥24 hrs; interfering with ADL  Colitis (Grade 3): severe abdominal pain, medical intervention indicated, peritoneal signs  Grade 4: life-threatening, perforation	Discontinue investigational product therapy per protocol 1.0 to 2.0 mg/kg/day methylprednisolone IV or equivalent Add prophylactic antibiotics for opportunistic infections Consider lower endoscopy	If improves:  Continue steroids until Grade 1, then taper over at least 1 month  If persists >3 to 5 days, or recur after improvement:  Add infliximab 5 mg/kg (if no contraindication), Note: Infliximab should not be used in cases of perforation or sepsis			
Dermatological irAEs					
Rash (NCI-CTCAE v4.03)	Management	Follow-up			
Grade 1 to 2 Covering ≤30% body surface area	Symptomatic therapy (eg, antihistamines, topical steroids) Continue investigational product therapy	If persists >1 to 2 weeks or recurs:  Consider skin biopsy  Delay investigational product therapy  Consider 0.5 to 1.0 mg/kg/day methylprednisolone IV or oral equivalent.  Once improving, taper steroids over at least 1 month, consider prophylactic antibiotics for opportunistic infections, and resume investigational product therapy  If worsens:  Treat as Grade 3 to 4			

 Table 4.
 Management of Immune-Related Adverse Events (irAEs)

Grade 3 to 4 Covering >30% body surface area; life threatening consequences  Pulmonary irAEs	Delay or discontinue investigational product therapy Consider skin biopsy Dermatology consult 1.0 to 2.0 mg/kg/day methylprednisolone IV or IV equivalent	If improves to Grade 1:  Taper steroids over at least 1 month and add prophylactic antibiotics for opportunistic infections  Resume investigational product therapy		
Grade of Pneumonitis (NCI-CTCAE v4.03)	Management	Follow-up		
Grade 1 Radiographic changes only	Consider delay of investigational product therapy Monitor for symptoms every 2 to 3 days Consider Pulmonary and Infectious Disease consults	Re-image at least every 3 weeks If worsens: Treat as Grade 2 or Grade 3 to 4		
Grade 2 Mild to moderate new symptoms	Delay investigational product therapy Pulmonary and Infectious Disease consults Monitor symptoms daily, consider hospitalization 1.0 mg/kg/day methyl-prednisolone IV or oral equivalent Consider bronchoscopy, lung biopsy	Re-image every 1 to 3 days  If improves:  When symptoms return to near baseline, taper steroids over at least 1 month and then resume investigational product therapy and consider prophylactic antibiotics  If not improving after 2 weeks or worsening:  Treat as Grade 3 to 4		
Grade 3 to 4 Severe new symptoms; New / worsening hypoxia; life-threatening	Discontinue investigational product therapy Hospitalize Pulmonary and Infectious Disease consults 2 to 4 mg/kg/day methylprednisolone IV or IV equivalent Add prophylactic antibiotics for opportunistic infections Consider bronchoscopy, lung biopsy	If improves to baseline:  Taper steroids over at least 6 weeks  If not improving after 48 hours or worsening:  Add additional immunosuppression (eg, infliximab, cyclophosphamide, intravenous immunoglobulin, or mycophenolate mofetil)		
Hepatic irAEs				
Liver Function Tests (LFT) Increase (NCI-CTCAE v4.03)	Management	Follow-up		
Grade 1 Grade 1 AST or ALT > ULN to 3.0 x ULN and/or Total bilirubin > ULN to 1.5 x ULN	Continue investigational product therapy	Continue liver function monitoring If worsens: Treat as Grade 2 or 3 to 4		

 Table 4.
 Management of Immune-Related Adverse Events (irAEs)

Grade 2	Delay investigational product therapy	If returns to baseline:	
AST or ALT >3.0 to ≤5 x ULN and/or total bilirubin >1.5 to ≤3 x ULN	Increase frequency of monitoring to every 3 days	Resume routine monitoring, resume investigational product therapy  If elevations persist >5 to 7 days or worsen:  0.5 to 1 mg/kg/day methylprednisolone or oral equivalent and when LFT returns to Grade 1 or baseline, taper steroids over at least 1 month, consider prophylactic antibiotics for opportunistic infections, and resume investigational product therapy	
Grade 3 to 4 AST or ALT >5 x ULN and /or total bilirubin >3 x ULN	Discontinue investigational product therapy Increase frequency of monitoring to every 1 to 2 days 1.0 to 2.0 mg/kg/day methylprednisolone IV or IV equivalent Add prophylactic antibiotics for opportunistic infections Consult gastroenterologist Consider obtaining MRI/CT scan of liver and liver biopsy if clinically warranted	If returns to Grade 2:  Taper steroids over at least 1 month  If does not improve in >3 to 5 days, worsens or rebounds:  Add mycophenolate mofetil 1 gram (g) twice daily  If no response within an additional 3 to 5 days, consider other immunosuppressants per local guidelines	
Endocrine irAEs			
Endocrine irAEs Endocrine Disorder	Management	Follow-up	
	Continue investigational product ther If TSH <0.5 x LLN, or TSH >2 x UL		

Table 4. Management of Immune-Related Adverse Events (irAEs)

Suspicion of adrenal crisis (eg, severe dehydration, hypotension, shock out of proportion to current illness)	Delay or discontinue investigational product therapy Rule out sepsis Stress dose of IV steroids with mineralocorticoid activity	
	IV fluids Consult endocrinologist If adrenal crisis ruled out, then treat as above for symptomatic endocrinopathy	

ADL=activities of daily living, ALT=alanine aminotransferase, AST=aspartate aminotransferase, irAE=immune-related adverse event, IV=intravenous, LLN=lower limit of normal, MRI=magnetic resonance imaging, NCI-CTCAE=National Cancer Institute-Common Terminology Criteria for Adverse Events, NSAIDs=nonsteroidal anti-inflammatory drugs, T4=thyroxine, TSH=thyroid-stimulating hormone, ULN=upper limit of normal.

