# 5.4.5.6. Dose Reductions, Interruptions and Discontinuation Criteria

# 5.4.5.6.1. Part A Monotherapy

Following dose interruption, cycle delay due to toxicity, or observation of late immune related DLTs such that the current dose of treatment is now considered to be above the MTD (see Section 3.2.1 Late Immune Related DLTs), the PF-04518600 dose may need to be reduced when treatment is resumed.

No specific dose adjustments are recommended for Grade 1/2 treatment-related toxicity. However, investigators should always manage their patients according to their medical judgment based on the particular clinical circumstances.

Dose reduction of PF-04518600 by 1 and, if needed, 2 dose levels will be allowed depending on the type and severity of toxicity observed. Patients enrolled in the first (0.01 mg/kg) cohort should be discontinued from the study if dose reduction is required. Patients requiring more than 2 (or 1 for the first cohort) dose reductions will be discontinued from the treatment and entered into the follow-up phase, unless otherwise agreed between the investigator and the sponsor. For example, if a patient has clear signs of clinical benefit, and if the investigator considered it to be in the best interest of the patient, they may be allowed to stay on study at a further reduced dose after recovery and appropriate dose interruption. All dose modifications/adjustments must be clearly documented in the patient's source notes and CRF.

Once a dose has been reduced for a given patient, all subsequent cycles should be administered at that dose level, unless further dose reduction is required. Dose re-escalation is not allowed

Patients experiencing a DLT may resume dosing at the next lower dose level once adequate recovery is achieved. No dose reductions are planned for patients experiencing toxicities other than those listed as DLTs. However, patients experiencing recurrent and intolerable Grade 2 toxicity may resume dosing at the next lower dose level once recovery to  $\leq$  Grade 1 or baseline is achieved.

Recommended dose reductions are illustrated in Table 5.

Table 5. Dose Modification for Drug Related Toxicity at Start of Subsequent Cycle in Part A

Event	Action

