Grade 3 or 4 non-hematologic toxicity considered related to PF-04518600 per investigator judgment (including persistent nausea, vomiting, diarrhea despite optimal medical therapy), excluding clinically manageable electrolyte abnormalities.	
 
Hold PF-04518600 infusion until recovery to Grade 0-1 or baseline and reduce by 1 dose level.
 
If toxicity (Grade 3-4) reoccurs despite reduction, patient may be dose reduced again by 1 more dose level upon recovery to Grade 0-1 or baseline.
 
Prompt palliative and supportive measures mandated per local standard of care (eg, antiemetic).
 
Patients who experience Grade 4 non hematologic toxicities despite intervention should be discontinued from the study, unless restarting treatment at reduced dose level is in the patient's best interest per investigator judgment and after consultation with Pfizer's medical monitor (eg, clear clinical benefit and no alternative treatment options).
 

Hematologic toxicity considered related to PF-04518600 per investigator judgment  • Grade 4 neutropenia, ie, ANC <500 mm³ (1.0 x 10  /L) for more than 7 days; or,  • Febrile neutropenia, ie, fever >38.3°C or a sustained temperature of ≥38°C (100.4°F) with ANC <1000/mm³; or,  • Grade 4 Thrombocytopenia, ie, PLTS <25,000 mm³ (25.0 x 10  /L); or,  • Grade 3 Thrombocytopenia, ie, PLTS <50,000 mm³ (50.0 x 10  /L) with bleeding.	
 
Hold PF-04518600 until recovery of ANC to         ≥1.0 x 10^9/L (1,000 cells/mm³) and platelets         ≥75 x 10^9/L (75,000 cells/mm³). For HCC         patients, a lower threshold for platelets can be         considered after discussion with the sponsor's         medical monitor (eg, 40,000 cells/mm³),         depending on the shift from baseline.
 
Reduce PF-04518600 by 1 dose level.
 
If toxicity reoccurs (grades a described on the left         side) despite dose reduction, patient may either be         held until recovery and continuation at same dose,         or undergo further dose reduction by 1 more dose         level.
 

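### In Part A, a related Grade 3 immune pneumonitis or liver-test increase carries two incompatible study-drug instructions: Table 4 says discontinue, Table 5 says hold and resume one level lower

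*Protocol*

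**What the plan says.** Section 5.4.5.4 applies to both parts of the study. Its severity bullets, including "Persistent Grade 2: manage similar to Grade 3 to 4 AE", deal with symptomatic treatment, steroids and monitoring, and the section then directs irAE treatment to Table 4. Table 4 adds study-drug actions. At Grade 3 to 4 these are:

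- Pneumonitis: "Discontinue investigational product therapy Hospitalize Pulmonary and Infectious Disease consults".
- LFT increase: "Discontinue investigational product therapy Increase frequency of monitoring to every 1 to 2 days".
- Diarrhea/colitis: "Discontinue investigational product therapy per protocol".
- Rash: "Delay or discontinue investigational product therapy Consider skin biopsy".

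Part A has a second set of rules in Section 5.4.5.6.1. Table 5 there covers any Grade 3 or 4 non-hematologic toxicity that the investigator considers related, and excludes only manageable electrolyte abnormalities. Its instruction is "Hold PF-04518600 infusion until recovery to Grade 0-1 or baseline and reduce by 1 dose level". The text of the section adds: "Patients experiencing a DLT may resume dosing at the next lower dose level once adequate recovery is achieved".

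Section 5.4.5.6.2 (Part B) repeats the direction to Table 4 for irAEs and limits Table 6 to the remaining drug-related toxicities. Section 5.4.5.6.1 does neither.

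**The concern.** A Part A patient who recovers from a related Grade 3 immune pneumonitis or hepatitis is taken off drug under Table 4 and re-exposed at a lower dose under Table 5. Two sites acting in good faith could do opposite things.

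Part A2 has the RP2D and further characterization of safety and tolerability as its primary objectives. SAP Section 7.2.3 tabulates treatment discontinuations with reasons, and dose reductions by dose level. The same event could therefore count as a discontinuation at one site and as a dose reduction at another.

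**Working it through.** The check is mainly a comparison of rules, with one short calculation for size.

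**1. Does the same event fall under both tables?** Yes. An immune pneumonitis or LFT increase that the investigator judges immune-mediated falls under Table 4. If it is also judged related to PF-04518600 and is Grade 3, it meets the entry condition of Table 5, whose exclusion does not mention irAEs. It can also fall under the sentence on resuming after a DLT. Section 3.2 counts clinically significant Grade 3 or higher non-hematologic toxicity as a DLT, and Section 3.2.1 applies the same grading to immune-related events from Day 29 through the 98-day period.

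**2. Part A rules side by side**

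| Event | Table 4 | Table 5 and Section 5.4.5.6.1 | Can both be followed? |
|---|---|---|---|
| Grade 3 pneumonitis | Discontinue; taper steroids on improvement; no resume step | Hold to Grade 0-1 or baseline, then reduce one level | No |
| Grade 3 LFT increase | Discontinue; taper steroids on improvement; no resume step | Same | No |
| Grade 3 colitis | Discontinue 'per protocol'; no resume step | Same; persistent diarrhea is named | Unclear |
| Grade 3 rash | Delay or discontinue; resume at Grade 1 | Same | Largely; they differ on dose reduction |
| Grade 4 despite intervention | Discontinue (rash: delay or discontinue) | Discontinue, with a best-interest exception | Largely |
| Persistent Grade 2 | Colitis, rash and LFT rows: steroids, then resume; non-responding colitis or pneumonitis moves to Grade 3 to 4 handling | Table 5 has no Grade 2 row; the text covers only recurrent, intolerable Grade 2 | Not opposite in general |

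**3. Could 'discontinue' in Table 4 mean 'hold'?** Not easily. The Grade 2 colitis, pneumonitis and LFT rows say delay and later resume. The Grade 3 to 4 rash row says delay or discontinue and has a resume step. The pneumonitis and LFT rows at Grade 3 to 4 say only discontinue. The table appears to choose its verbs deliberately.

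**4. Size.** Section 1.2.1.3 reports 52 patients treated in Part A1 and one related Grade 3 event, a GGT increase. Table 4's hepatic row is graded on AST, ALT and total bilirubin, so that event lies outside it. The relevant count is x = 0 of n = 52.

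- Exact (Clopper-Pearson) 95% upper limit for x = 0: 1 − 0.025^(1/52) = 1 − exp(−3.689/52) = 1 − exp(−0.0709) = 0.0685, reported as 6.8% (unrounded 6.848%).
- Per Part A2 arm of 20: 20 × 0 = 0 up to 20 × 0.0685 = 1.4 patients.
- Weight of one patient: 1/20 = 5 percentage points of an arm's discontinuation or dose-reduction rate.

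**The case against.** The best reply is that the specific rule governs the general one. Section 5.4.5.4 sends irAEs to Table 4 for all parts, Table 5 is generic, and the DLT sentence only says that patients may resume. That much stands: Table 4 is the likelier intended rule, and it would be wrong to infer that Part A has no pointer to it.

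It does not remove the conflict. Table 5 is worded as an instruction, not a permission, and its one stated exclusion is not irAEs. Section 5.4.5.5 also says to interrupt or delay at Grade 3 or 4, without an irAE exception. Part B was given an explicit division although it needs one less, since Table 6 already defaults to permanent discontinuation at Grade 3.

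It is also fair to say that the consequence is slight. Part A2's primary endpoints are adverse events and laboratory abnormalities, the SAP summaries are non-inferential, and sponsor and investigators discuss adverse events on an ongoing basis.

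Three wider readings are tempting, and the documents do not support them:

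- **That the conflict extends to persistent Grade 2.** The bullet "Persistent Grade 2: manage similar to Grade 3 to 4 AE" names no study-drug action, and three Table 4 Grade 2 rows resume treatment after steroids. Escalation is conditional; for colitis it reads "If worsens or persists >3 to 5 days with oral steroids: Treat as Grade 3 to 4".
- **That it covers every Grade 3 to 4 irAE.** Table 5 itself discontinues for Grade 4 toxicity despite intervention, rash can be delayed under both tables, and the colitis row's 'per protocol' may defer to other sections.
- **That the Part A1 rate is 1 in 52, or about 0.4 per arm (20 × 1/52).** The single event was a GGT rise, which Table 4's hepatic row does not grade.

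**Conclusion.** The point holds, as a minor one, for two event types: related Grade 3 immune pneumonitis and related Grade 3 LFT increase in Part A. Grade 3 colitis is ambiguous.

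The expected number is small: 0 of 52 in Part A1, compatible with up to 6.8%, or up to 1.4 patients per arm of 20. This assumes that Section 1.2.1.3 (cut-off 24 May 2017) lists all related Grade 3 events and that Part A2 resembles Part A1. The second assumption is loose. Part A1 mixed tumor types and doses, whereas Part A2 enrolls only HCC patients. They may enter with AST and ALT up to 5.0 × ULN, the value above which Table 4's Grade 3 to 4 hepatic row begins.

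DLT counting and the MTD are unaffected, because an event counts as a DLT on its nature and grade, whatever is then done with study drug. What is affected is whether a patient is re-exposed, and how the event appears in the discontinuation and dose-reduction tables.

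**What to change.** Make two edits to Section 5.4.5.6.1 in the next amendment:

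1. Add the division that Part B already has: irAEs are managed under Table 4 of Section 5.4.5.4, and Table 5 is limited to drug-related toxicity other than irAEs.
2. Qualify the sentence on resuming after a DLT with the condition that Table 4 does not require discontinuation.

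This agrees with the existing direction in Section 5.4.5.4. It also largely settles colitis, since 'per protocol' could then no longer lead back to Table 5. Data collection and the SAP do not change.

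The cost is clinical: Part A patients who recover from a Grade 3 pulmonary or hepatic irAE lose the option of redosing at a lower level. If the sponsor wants to keep that option, it should be written as an explicit Part A exception in Table 4 in place of these edits, so that one rule remains.

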### **5.4.5.5. Dose Delay**

Re-treatment following treatment interruption for treatment related toxicity or at the start of any new cycle may not occur until all of the following parameters have been met:

- ANC  $\ge 1,000/\text{mm}^3$ .
- Platelets count ≥50,000/mm³. HCC only: based on investigator judgment, after consultation with sponsor's medical monitor, change from baseline will be considered, and levels of ≥25,000/mm³ may be acceptable.
- Non-hematologic toxicities have returned to baseline or Grade ≤1 severity (or, at the investigator discretion, Grade ≤2 if not considered a safety risk for the patient).

If a treatment delay results from worsening of hematologic or biochemical parameters, the frequency of relevant blood tests should be increased as clinically indicated. Patients experiencing Grade 3 or 4 potentially treatment related toxicity or intolerable Grade 2 toxicity despite supportive care should have their treatment interrupted/delayed. Appropriate follow-up assessments should be done until adequate recovery (or until deemed irreversible) occurs as assessed by the Investigator.

If these conditions are met within 2 weeks of treatment interruption or cycle delay, PF-04518600 or PF-04518600/utomilumab may be resumed. For monotherapy, please refer to Section 5.4.5.6.1 (Dose Reductions, Interruptions and Discontinuation Part A Monotherapy) for adverse events requiring dose reduction at the time of treatment resumption. For combination therapy, intrapatient dose reduction will not be permitted (see Section 5.4.5.6.2 Dose Reductions, Interruptions and Discontinuation Part B Combination Therapy).

If these conditions are not met, treatment resumption must be delayed up to a maximum of 4 weeks. If these parameters have not been met after 4 weeks of dose interruption or 4 weeks of new cycle delay, permanent discontinuation of treatment with PF-04518600 or PF-04518600/utomilumab should be considered. Treatment resumption for patients

recovering from treatment-related toxicity after 4 weeks of treatment interruption or cycle delay can be considered only if the patient is deemed to be deriving obvious clinical benefit per the investigator's best medical judgment and needs to be agreed between the investigator and the sponsor.

If a treatment interruption continues beyond Day 14 of the current cycle, then the day when treatment is restarted will be counted as Day 1 of the next cycle.

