# 5.4.5.6.2. Part B Combination Therapy

Intrapatient dose reductions are not permitted during the combination therapy with PF-04518600 and utomilumab unless, in discussion with the sponsor, a dose combination level is deemed to be above the determined MTD for the combination.

Given the expected similarities of side effect profile and mechanism between the two co-stimulation monoclonal antibodies, both treatments must be interrupted or discontinued together. Patients will not be permitted to continue treatment with one agent, while the other agent is either interrupted or permanently discontinued. If infusion related reactions are observed following the administration of the first agent, administration of the second agent will be withheld until symptoms resolve (see Section 5.4.5.1 Infusion Reactions).

Treatment of irAEs should follow guidelines set forth in Table 4 in Section 5.4.5.4 Recommended dose modifications for any other drug-related toxicity are illustrated in Table 6.

Table 6. Treatment Interruptions/ Discontinuations for Drug Related Toxicity at Start of Subsequent Cycle

Toxicity	NCI CTCAE Severity Grade	Treatment Modifications
Hematologic abnormalities.	Grade 3	
 
Withhold until recovery to Grade 1 or better.
 
If toxicity does not resolve to Grade 1 or better within 4 weeks of last infusion, consider permanent discontinuation after consultation with the sponsor.
 
Upon the second occurrence of the same Grade 3 toxicity that does not resolve to Grade ≤1 by the next administration, treatment must be permanently discontinued.
 

	Grade 4	Permanent discontinuation.     Exceptions are:     Single laboratory values out of normal range that are unlikely related to investigational product (s) as assessed by the Investigator, do not have any clinical correlate, and resolve within 7 days with adequate medical management.
Infusion-related reaction.	Grade 1-4	• See Section 5.4.5.1 and Appendix 4.
Hypersensitivity reaction.	Grade 1-4	• See Section 5.4.5.2 and Appendix 4.

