Other non-hematologic toxicities and laboratory abnormalities.	Grade 2	
 
If toxicity resolves to Grade ≤1 by the next administration, treatment may continue.
 
If toxicity does not resolve to Grade ≤1 by the next administration despite optimal treatment, the next infusion should be omitted. If at the end of 4 weeks of dose holding, the event has not resolved to Grade ≤1, the patient should permanently discontinue treatment (except for hormone deficiencies that can be managed by replacement therapy and for which up to 2 additional subsequent doses may be omitted).
 

Table 6. Treatment Interruptions/ Discontinuations for Drug Related Toxicity at Start of Subsequent Cycle

Toxicity	NCI CTCAE Severity Grade	Treatment Modifications
	Grade 3	Permanent discontinuation, Exceptions are:
		
 
Transient (≤6 hours) flu-like symptoms or fever, which is controlled with medical management.
 
Transient (≤24 hours) fatigue, local reactions, headache that resolves to Grade ≤1.
 
Nausea and vomiting controlled by medical therapy.
 
Diarrhea, skin toxicity, or liver function test (ALT, AST, or Gamma-glutamyltransferase [GGT]) that resolves to ≤ Grade 1 in less than 7 days after medical management (eg, immunosuppressant treatment) has been initiated.
 
Amylase or lipase abnormality that is not associated with symptoms or clinical manifestations of pancreatitis.
 
Tumor flares phenomenon defined as local pain, irritation, or rash localized at sites of known or suspected tumor.
 
Non hematologic laboratory abnormality that do not require medical intervention or hospitalization.
 
Single non hematologic laboratory values out of normal range that are unlikely related to treatment as assessed by the Investigator, do not have any clinical correlate, and resolve to ≤ Grade 1 within 7 days with adequate medical management.
 

	Grade 4	Permanent discontinuation, Exceptions are:
		
 
Non hematologic laboratory abnormality that does not require medical intervention or hospitalization. Single non hematologic laboratory values out of normal range that are unlikely related to treatment as assessed by the Investigator, do not have any clinical correlate, and resolve within 7 days with adequate medical management.
 
Amylase or lipase abnormality that is not associated with symptoms or clinical manifestations of pancreatitis.
 

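### Section 5.4.5.5 and Tables 5 and 6 set different recovery thresholds for the same start-of-cycle decision, and nothing says which prevails

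*Protocol*

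**What the plan says.** **Section 5.4.5.5 (Dose Delay).** The section opens: "Re-treatment following treatment interruption for treatment related toxicity or at the start of any new cycle may not occur until" its listed conditions are all met. These are:

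- ANC of at least 1,000/mm³.
- Platelets: "Platelets count ≥50,000/mm³. HCC only: based on investigator judgment". For HCC patients, after consultation with the medical monitor and with change from baseline considered, "levels of ≥25,000/mm³ may be acceptable".
- Non-hematologic toxicity at baseline or Grade 1 or lower, or "at the investigator discretion, Grade ≤2 if not considered a safety risk for the patient".

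If the conditions are met within 2 weeks, monotherapy or the combination may restart. Grade 3 or 4 toxicity that may be treatment-related leads to interruption or delay. After 4 weeks of interruption or cycle delay, permanent discontinuation is to be considered. Later resumption is possible with clear clinical benefit and sponsor agreement.

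**Table 5 (Section 5.4.5.6.1, Part A).** After its listed hematologic events, drug is held until ANC is at least 1,000/mm³ and platelets are at least "75,000 cells/mm³". For HCC patients a lower platelet value can be considered after discussion with the sponsor's "medical monitor (eg, 40,000 cells/mm³"), depending on the shift from baseline. After related Grade 3 or 4 non-hematologic toxicity, drug is held until Grade 0-1 or baseline.

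**Table 6 (Section 5.4.5.6.2, Part B).**

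- Grade 2 non-hematologic: "If toxicity does not resolve to Grade ≤1 by the next administration despite optimal treatment, the next infusion should be omitted". If the event is unresolved after 4 weeks of holding, treatment should stop permanently, hormone deficiencies excepted.
- Grade 4 hematologic and Grade 3 or 4 non-hematologic: permanent discontinuation, with listed exceptions.
- Grade 3 hematologic: "If toxicity does not resolve to Grade 1 or better within 4 weeks of last infusion", permanent discontinuation is to be considered after consulting the sponsor.

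**The concern.** The titles of both tables place them at the start of a subsequent cycle, which is also where Section 5.4.5.5 says it applies. A site deciding whether to give the next infusion can therefore reach opposite answers from two parts of one protocol, both of which appear to govern.

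The first issue is patient safety and consistent care. The analysis is also affected. Section 3.2 allows toxicities that cause significant dose delay, as described in Section 5.4.5.5, to be considered as DLTs, so the point at which a delay ends can bear on DLT review in Parts A1 and B1. Section 9.3.1 continues DLT assessment in Part A2. SAP Section 7.2.3 summarizes cycle delays, interruptions, reductions and time on treatment by dose level. If sites apply different thresholds, those summaries pick up variation unrelated to dose, in cohorts of about 10 to 20 patients.

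**Working it through.** The plan has no figure to reproduce here. The check sets the passages side by side for the same patient state.

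| Situation | Section 5.4.5.5 | Table 5 or 6 |
|---|---|---|
| (a) Part A, after a Table 5 hematologic event, platelets 50,000 to 74,999/mm³ | Resumption permitted | Table 5: hold |
| (b) Part A, related Grade 3-4 non-hematologic toxicity now at Grade 2, baseline lower | Resumption permitted at investigator discretion | Table 5: hold until Grade 0-1 or baseline |
| (c) Part B, Grade 2 non-hematologic toxicity persisting at the next dose | Re-dosing permitted at investigator discretion | Table 6: omit; stop permanently if unresolved after 4 weeks of holding |
| (d) Part B, Grade 4 hematologic or Grade 3-4 non-hematologic, outside the exceptions | Interrupt or delay, with resumption on recovery | Table 6: permanent discontinuation |
| (e) Part B, Grade 3 hematologic, 4-week limit | Counted from interruption or cycle delay | Table 6: counted from the last infusion |

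**Row (a).** The thresholds differ by 75,000 − 50,000 = 25,000/mm³. Table 5's hold has four triggers: Grade 4 neutropenia for more than 7 days, febrile neutropenia, Grade 4 thrombocytopenia, and Grade 3 thrombocytopenia with bleeding. Grade 3 thrombocytopenia without bleeding is not a trigger, so it creates no conflict. For HCC patients in this range the only difference is procedural: Table 5 calls for discussion with the medical monitor before going below its default, and 5.4.5.5 requires none at 50,000/mm³ or above. This can arise at a patient's own baseline, because Section 4.1.1 admits HCC patients at 60,000/mm³. The ANC recovery value, 1,000/mm³, is the same in both places.

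**Row (b).** Table 5's non-hematologic row is not restricted by tumor type, so it covers Part A2 as well as A1.

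**Row (c).** Section 5.4.5.6.2 sends immune-related events to Table 4, and Table 6 sends infusion and hypersensitivity reactions to Sections 5.4.5.1 and 5.4.5.2 and Appendix 4. The conflict concerns the remaining Grade 2 non-hematologic toxicities.

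**Row (e).** The two clocks are apart by the time from the last infusion to the start of the hold, which depends on when in the cycle the hold begins.

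**Precedence.** Section 5.4.5.5 refers to 5.4.5.6.1 for events requiring dose reduction, and to 5.4.5.6.2 for the rule against intrapatient reduction in the combination. Neither reference concerns the recovery threshold, and no other text ranks the section against the tables.

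**The case against.** The best defence is that 5.4.5.5 sets a general minimum, worded as a bar on dosing until its conditions are met, and that the tables add stricter rules for particular events. A site that always follows the stricter text breaches neither, and permission to resume is not an instruction to dose. Row (d) in particular can be read as interrupt first, then stop.

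That reading is workable, but the protocol does not state it. Section 5.4.5.5 goes on to permit resumption once its own conditions are met, and names the combination when it does so. For toxicities under Table 6, the minimum reading also leaves the Grade 2 discretion with little to act on.

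The objection is right on reach. A reader might infer that any Part A patient at 50,000 to 74,999/mm³ is caught; only those recovering from a listed event are. Part A2 randomizes HCC patients, so the firm platelet conflict falls mainly on non-HCC patients in A1. By 24 May 2017, 52 of about 58 planned A1 patients had been treated, with one Grade 3 treatment-related event (a GGT increase) and no DLTs (Sections 1.2.1.3 and 3.1.1.1). The documents therefore do not show that bleeding, toxicity or discontinuation rates have depended on which text a site followed.

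A reader might also set the HCC values of 25,000 and 40,000/mm³ against each other as a 15,000/mm³ gap. The first is a level that may be acceptable and the second is an example. Both involve the medical monitor and change from baseline, so they do not contradict.

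**Conclusion.** The inconsistency is real and confined to the five situations in the table. Rows (a), (b) and (c) are the firmest: for the same patient, one text permits dosing and the other withholds it. Row (d) is a difference between interrupting and stopping. Row (e) is minor, since both texts only ask that discontinuation be considered. Together they reach all four parts: (a) and (b) in Part A, (c) to (e) in Part B.

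Two stronger readings of the 4-week limit are not supported. One is that it has three start points. A cycle delay in 5.4.5.5 starts at the scheduled infusion, which is Table 5's clock, and Table 6's Grade 2 row counts weeks of holding, which fits the interruption clock. Only Table 6's Grade 3 hematologic row stands apart. The other is a contrast of day 28 with day 42 after the last infusion, taken from Tables 6 and 5. That sets a Part B row against a Part A row, and no patient is governed by both.

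The conclusion rests on the wording alone. It assumes no instruction outside these documents already sets precedence, and it takes no view on which threshold is right. How often the conflict will arise cannot be estimated from the documents. It should be corrected because dosing decisions depend on it.

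**What to change.** Reconcile Section 5.4.5.5 with Tables 5 and 6 for rows (a) to (d), or add one sentence stating which text prevails for the events the tables list. The wording should settle whether the Grade 2 discretion applies after a Table 5 non-hematologic event and to toxicities under Table 6, and whether an HCC patient at 50,000 to 74,999/mm³ after a Table 5 event needs medical-monitor discussion. Give the 4-week limit for Part B one start point. The sponsor chooses every value and rule.

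The cost is protocol wording in one section and two tables, with no added procedures or patients.
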